7.2. Summary of Analysis Methods

Primary Objective	Outcome	Comp. w/ control?	Analysis Methods
1) To assess the feasibility of uptake amongst people with 'high risk' or 'very high risk' type 2 diabetes .	offered Fresh Start vs. enrolled	No	Frequency and percentage enrolled presented
	enrolled vs. downloading app	No	Frequency and percentage downloading presented
2) To assess the usability of Fresh Start amongst people with 'high risk' or 'very high risk' type 2 diabetes .	VGCs attended	No	Summary stats of VGCs attended overall and per unit time
	emails metrics as section 7.5.2	No	Frequency and percentages presented
	blood glucose measurements recorded	No	Summary stats of meas. recorded by patient overall and per unit time
	blood pressure measurements recorded	No	Summary stats of meas. recorded by patient overall and per unit time
	weight* measurements recorded	No	Summary stats of meas. recorded by patient overall and per unit time
	Diabetes Distress Scale measurements recorded	No	Summary stats of meas. recorded by patient overall and per unit time
4) To assess the acceptability of Fresh Start amongst people with 'high risk' or 'very high risk' type 2 diabetes .	Interviews with patients (x10)	No	As per ICHP team
5) To assess the acceptability of Fresh Start amongst HCPs .	Interviews with healthcare professionals (HCPs, x10)	No	As per ICHP team
6) To assess the cost-effectiveness of delivering Fresh Start.	primary care appointments per patient (as recorded)	Yes	Summary stats of no appts. attended per patient up to 6 months post enrollment

Primary Objective	Outcome	Comp. w/ control?	Analysis Methods
			Comparison between groups via poisson mixed model
	Cost per appointment per patient	Yes	Summary stats of appt. cost per patient. Comparison between groups via mixed model
	Cost of equipment per patient	No	Summary stats of overall cost per patient.

Secondary Objective	Outcome	Comp. w/ control?	Analysis Methods
1) To assess the safety of Fresh Start.	Number of deaths	Yes	Frequency and percentages presented up to 6 months post enrollment
	Number of emergency department admissions	Yes	Frequency and percentages presented up to 6 months post enrollment
	Number of hospital admissions	Yes	Frequency and percentages presented up to 6 months post enrollment. Difference presented with 95% CI
2) To assess the impact of Fresh Start on clinical outcomes .	HbA1c	Yes	Summary stats of HbA1c by visit (BL, W12, M6) Comparison within & between groups via mixed model
	Lipids, incl. LDL and non-HDL cholesterol	Yes	Summary stats of Lipids by visit (BL, W12, M6) Comparison within & between groups via mixed model (if available)
	Weight (or BMI as appropriate)	Yes	Summary stats of Weight by visit (BL, W12, M6) Comparison within & between groups via mixed model
	Diabetes Distress Scale score (DDS[iii])	No	Summary stats of DDS at per visit (M0, M1, M2, M3). Comparison within groups via mixed model (if available)
	Blood glucose time-in-range	Yes	Summary stats of days in range up to 6 months post enrollment

Imperial Clinical Trials Unit	SUB-STUDY SAP TEMPLATE – SUB-ANALYSES AND OBSERVATIONAL STUDIES	SOP_TEM_BS002
-------------------------------	---	---------------

Secondary Objective	Outcome	Comp. w/ control?	Analysis Methods
			Comparison against control via mixed model (if available)
	Systolic blood pressure (SBP)	Yes	Summary stats of SBP Comparison between groups via mixed model (if available)

7.3. Patient Flow (CONSORT)

A CONSORT diagram covering patient flow into the study will be produced.

7.4. Patient Demographics & Baseline Readings

Tables summarising demographics are to be produced for both the FreshStart and propensity-matched groups. Additional output will be produced dichotomising the FreshStart group into 2 subgroups; those that used the HUMA device, and those that did not.

Demographics will cover Age, Gender, Ethnicity, Deprivation Score & Location

7.5. Primary Analysis Methodology

7.5.1. Feasibility of uptake amongst people with ‘high risk’ or ‘very high risk’ type 2 diabetes

For both definitions of comparative measures as defined in 6.2.1, frequencies of each category will be presented with proportions established as percentages presented to 1 decimal place (dp)

- Patients enrolled vs patients initially offered device
- Patients collecting Fresh Start data vs patients enrolled.

7.5.2. Usability of Fresh Start amongst people with ‘high risk’ or ‘very high risk’ type 2 diabetes.

Summary statistics denoting mean, sd, median, 1st/3rd quartiles, and minimum/maximum events per patient and per patient per unit time (day/week as appropriate) will be derived. Results will be presented as mean (SD) for normally distributed data and median [Q1-Q3] for skewed:

- Number of **Video Group Consultations (VGC)** attended per patient
- Number of **Blood Glucose measurements** recorded per patient within HUMA
- Number of **Blood Pressure measurements** recorded per patient within HUMA
- Number of **Weight measurements** recorded per patient within HUMA
- Number of **Diabetes Distress Score (DDS)** measurements recorded per patient within HUMA

For Fresh Start emails, the following frequencies will be presented, any additional information may also be presented:

- Number of patients that interacted with all emails

- Number of patients that interacted with no emails
- Interactions per email (click rates)

7.5.3. Acceptability of Fresh Start amongst people with 'high risk' or 'very high risk' type 2 diabetes.

Interviews are to be carried out by members of the research team from the Institute of Global Health Innovation (IGHI) at Imperial College London and will form part of a qualitative analysis. Interviews conducted with participants will be analysed using NVivo, where responses will undergo thematic analysis using an inductive approach to derive key themes.

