5.5. Sample Size

The study will seek to collect and analyse data from a minimum of 300 participants to Fresh Start. With an estimated enrolment rate of 20%, 1,500 eligible patients will need to be identified and we will be able to estimate this rate within a 95% confidence interval of +/-3%, accounting for variance inflation due to clustering with the assumption of 10 GP practices and Intraclass Correlation Coefficient (ICC) of 0.05.

The study's secondary objectives are exploratory only and will not be demonstrated to a level of statistical significance in this study.

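### The study is sized on a clustered 95% confidence interval for the enrolment rate, but the SAP's planned output reports that rate only as a count and a percentage

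*SAP*

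**What the plan says.** SAP 5.5, in the same words as protocol 3.3, sets a minimum of 300 participants and continues: "With an estimated enrolment rate of 20%, 1,500 eligible patients will need to be identified". The justification is precision: "we will be able to estimate this rate within a 95% confidence interval of +/-3" per cent, "accounting for variance inflation due to clustering with the assumption of 10 GP practices and Intraclass Correlation Coefficient (ICC) of 0.05". No other sizing basis is given, and for the rest the section states that "The study's secondary objectives are exploratory only and will not be demonstrated to a level of statistical significance in this study".

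SAP 7.5.1 covers both uptake measures (enrolled among offered, and collecting data among enrolled): "frequencies of each category will be presented with proportions established as percentages presented to 1 decimal place (dp". The corresponding entry in SAP 7.2 is "Frequency and percentage enrolled presented". SAP 7.1.1 calls the primary endpoints descriptive. Protocol 3.11 gives categorical variables as frequencies and percentages. SAP Appendix 1 lists the two uptake outputs (3.1 and 3.2) with no table template.

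Elsewhere the SAP does plan what is missing here. Section 7.6.1 gives a 95% interval for the exploratory safety composite, and sections 7.5.5 and 7.6.2 allow for clustering by GP practice when modelling appointments, costs and clinical outcomes.

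**The concern.** The design criterion and the planned output do not meet. The study is sized so that one quantity, the enrolment rate, is known to a stated precision after allowing for practice clustering. An analyst who follows 7.5.1 and 7.2 will not calculate that precision.

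This matters because the missing interval cannot be recovered from what is reported. From a numerator and a denominator a reader can form only an ordinary binomial interval, which treats all patients offered as independent. If uptake differs between practices as much as the planning ICC assumes, that interval is far too narrow. Anyone using the result to judge likely uptake elsewhere would then believe the rate is known much better than it is.

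**Working it through.** **Inputs (SAP 5.5, protocol 3.3).** Enrolment rate p = 0.20; n = 1,500 patients; k = 10 practices; ICC = 0.05; 95% confidence. Derived: m = 1,500/10 = 150 patients per practice, and 0.20 × 1,500 = 300 enrolled. Two assumptions are mine: practices are of equal size, and all 1,500 identified patients are offered the service and so form the denominator.

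**Formula.** Design effect DE = 1 + (m − 1) × ICC. Half-width = multiplier × sqrt(p(1 − p) × DE / n).

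**The plan's own figure (±3%).**
- With m = 150: DE = 1 + 149 × 0.05 = 8.45. Half-width = 1.96 × sqrt(0.16 × 8.45 / 1,500) = 0.0588, or 5.9 points. This does not reproduce ±3%.
- With m = 30 (enrolled rather than offered patients per practice): DE = 1 + 29 × 0.05 = 2.45. Half-width = 1.96 × sqrt(0.16 × 2.45 / 1,500) = 0.0317, which rounds to 3%. This may be where the figure comes from, but it mixes two denominators.

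Whether ±3% is right is a separate question from whether any interval is reported. It is shown here because the interval, once added, will not match 5.5.

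**What a reported 20.0% would support.**

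| Interval | Half-width (points) | Range |
|---|---|---|
| Naive binomial, 1.96 × sqrt(0.16/1,500) | 2.0 | 18.0% to 22.0% |
| Clustered, normal multiplier | 5.9 | 14.1% to 25.9% |
| Clustered, t on 9 df (2.262) | 6.8 | 13.2% to 26.8% |

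The normal-multiplier clustered interval is sqrt(8.45) = 2.9 times as wide as the naive one. The effective sample size is 1,500/8.45 = 178.

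**Simulation check.** 40,000 runs with beta-binomial counts (an assumed form), 10 practices of 150, p = 0.20 and ICC 0.05. A t interval on practice rates (9 df) has a median half-width of 6.5 points and covers the true rate 94% of the time. The naive interval covers it 50% of the time.

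**Sensitivity to the ICC.**

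| ICC | DE | Clustered half-width, normal / t on 9 df (points) | Naive coverage |
|---|---|---|---|
| 0.05 | 8.45 | 5.9 / 6.8 | 50% |
| 0.02 | 3.98 | 4.0 / 4.7 | 67% |
| 0.01 | 2.49 | 3.2 / 3.7 | 79% |

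**Is the interval planned anywhere else?** No.
- The CONSORT diagram (SAP 7.3) covers patient flow into the study.
- Location (SAP 7.4) is a demographic of the Fresh Start and matched groups, not of those offered.
- The subgroups in SAP 7.7 are optional, and the one that is described is by adherence.
- The allowance in SAP 7.5.2 for additional information concerns emails.

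**The case against.** The strongest reply is that descriptive reporting is a declared choice, stated consistently in protocol 3.11 and SAP 7.1.1. There is no hypothesis and no progression threshold for uptake, so no planned decision turns on an interval. SAP 5.5, in the same document, already speaks of estimating the rate with a 95% interval, so the gap may be only a failure to carry that into 7.5.1. All of this is fair and it limits the severity. It does not remove the gap: an interval for a single proportion is estimation rather than testing, and the sponsor made its width the design criterion.

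Several stronger readings are tempting, and the documents do not support them:
- **That the plan contains an interval with about 50% coverage.** It contains no interval. That figure describes one a reader might add, and it depends on the planning ICC.
- **That the percentage is wrong because it ignores clustering.** Pooling patients gives a legitimate estimate of the overall rate. Clustering affects its standard error, and it is the uncertainty that goes unreported.
- **That one decimal place claims false precision.** This is formatting. Counts are shown alongside, and SAP 7.6.1 uses the same convention.
- **That practice-level results were promised and dropped.** No objective concerns variation between practices, and 5.5 refers only to the overall rate.
- **That the second uptake measure was also sized for.** No rate or precision is given for it anywhere.

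**Conclusion.** The point holds as an omission that should be corrected. The one quantity the study is sized to estimate with known precision has no measure of precision in the planned output, and nothing elsewhere in either document supplies it. The point estimate itself is unaffected.

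On the plan's inputs the missing half-width is about 5.9 points (6.5 to 6.8 with t on 9 degrees of freedom), against the 2.0 points a reader could work out from the counts. These sizes rest on the planning ICC of 0.05, equal practices and 1,500 patients offered. At an ICC of 0.01 the clustered half-width falls to 3.2 points (3.7 with t), still well above 2.0.

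**What to change.** In SAP 7.5.1 and 7.2, report the pooled enrolled/offered percentage with a 95% confidence interval adjusted for clustering by GP practice, using a method suited to about 10 clusters. State that the pooled patient-level rate is the estimand, so that the interval belongs to the percentage shown. Either of these would serve:
- a ratio estimator with cluster-robust variance and t on the number of practices minus 1 degrees of freedom;
- a random-intercept logistic model marginalised to the overall rate.

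A t interval on unweighted practice rates, or a random-intercept model left unmarginalised, estimates a different quantity when practices are unequal or vary in uptake.

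SAP 6.2.1 defines patients offered through a screening log kept by each PCN, and the documents do not confirm that it records the practice. Record the GP practice of each patient offered. If that is not possible, name the PCN as the cluster and set the degrees of freedom to match. Revisit the ±3% in 5.5 at the same time.

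Two additions would be useful, though 5.5 did not promise them: a small table of offered and enrolled by practice, and the same kind of interval for data collection among those enrolled. For the latter, with 300 enrolled, 30 per practice, ICC 0.05 and an assumed rate of 50% to 90%, the clustered half-width would be 8.9 to 5.3 points.

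The cost is one extra calculation, possibly one extra log field, and a reported precision less favourable than a bare percentage suggests.

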A 30-45 minute onboarding appointment will be completed by a practice nurse (PN), healthcare assistant (HCA) or a member of the administrative staff from the participant's primary care practice (at the discretion of the participating practice). The onboarding appointment can be completed via Microsoft Teams or face-to-face (at the discretion of the participant/primary care practice). The onboarding appointment will be used to explain the Huma app, video group consultations (VGCs), and the educational emails from Fresh Start. An onboarding guide and associated script has been developed to support the onboarding process.

Staff actions at primary care practice:

[figure not shown]
- Run one-to-one appointment via Microsoft Teams or a phone call
- Explain how to download and use Huma app & devices
- Book onto VGCs (x3)
- Sign up for Fresh Start emails

Fresh Start educational emails

Patients will be instructed to sign up for Fresh Start educational emails during the onboarding appointment. These emails will be twice-weekly and will ensure patients get supportive information and education on how to improve their type 2 diabetes.

Staff actions at primary care practice:

- Sign patients up to first two Fresh Start emails in onboarding call
- Sign patients up to full Fresh Start campaign in first VGC

Huma app, devices and Clinician Dashboard

The Huma app will enable participants to report their own clinical metrics, feelings, goals and behaviour activities (e.g. photos of food). At the onboarding appointment, participants will be instructed how to download the Huma app from the App Store (for iPhone users) or from the Google Play Store (for all other smartphones). Participants will also be shown how to use their blood pressure cuff and glucometer device, walked through the Diabetes Distress Scale questionnaire, and shown how to set goals and actions in the Huma app.

Imperial College London

[figure not shown]
Participants will be asked to enter results from their first measurements into the Huma app. The HCP who is running the onboarding appointment will check whether results have appeared on the Huma clinician dashboard. If data has not appeared HCPs are advised to contact Huma at [contact].

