6.1. Summary of Analysis Variables

Primary Objective	Outcome	Source	Freq.	Comp. w/ control?
1) To assess the feasibility of uptake amongst people with 'high risk' or 'very high risk' type 2 diabetes .	Patients offered Fresh Start vs. enrolled	EPR	Once	No
	Patients enrolled vs. downloading Huma app	Huma	Once	No
2) To assess the usability of Fresh Start amongst people with 'high risk' or 'very high risk' type 2 diabetes .	Number of VGCS attended	EPR	Every 4 weeks	No
	Number of Fresh Start emails opened	KD	Twice weekly	No
	Number of blood glucose measurements recorded	Huma	Daily	No
	Number of blood pressure measurements recorded	Huma	Daily	No
	Number of weight* measurements recorded	Huma	Daily	No
	Number of Diabetes Distress Scale measurements recorded	Huma	Monthly	No
3) To assess the acceptability of Fresh Start amongst people with 'high risk' or 'very high risk' type 2 diabetes .	Interviews with patients (x10)	Interview	At 12 weeks	No
4) To assess the acceptability of Fresh Start amongst HCPs .	Interviews with healthcare professionals (HCPs, x10)	Interview	After intervention	No
5) To assess the cost-effectiveness of delivering Fresh Start.	Number of primary care appointments per patient	EPR	Data extracted from EPR	Yes
	Cost per appointment per patient	EPR	Data extracted from EPR	Yes
	Cost of equipment per patient	Huma	N/A	No

* In the event where BMI data is more routinely collected the endpoint may be adjusted to BMI

Secondary Objective	Outcome	Source	Freq.	Compare with control?
1) To assess the safety of Fresh Start.	Number of deaths	EPR	Data extracted from EPR	Yes
	Number of emergency department admissions	WSIC	Data extracted from WSIC	Yes
	Number of hospital admissions	WSIC	Data extracted from WSIC	Yes
2) To assess the impact of Fresh Start on clinical outcomes .	HbA1c	EPR	Baseline, 12 weeks, 6 months	Yes
	Lipids, incl. LDL and non-HDL cholesterol	EPR	Baseline, 12 weeks, 6 months	Yes
	Weight *	EPR	Baseline, 12 weeks, 6 months	Yes
	Diabetes Distress Scale score (DDS[iii])	Huma	Monthly during service (and at 6 month follow-up appt.)	No
	Blood glucose time-in-range	Huma	Daily	Yes
	Systolic blood pressure (SBP)	Huma	Daily	Yes

* Note, if patient Height is also recorded BMI may be presented as an alternative

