6.2. Primary Analysis Variables

6.2.1. Feasibility of uptake amongst people with ‘high risk’ or ‘very high risk’ type 2 diabetes

Feasibility of uptake is to be determined by the following measures:

- Patients enrolled with Fresh Start in comparison to those offered the Fresh Start service. Enrolment is defined as all patients entered within the study dataset. Offered is defined as those contacted about Fresh Start by their PCN by phone call or SMS and recorded in the Screening Log for that PCN.
- Patients collecting Fresh Start data in comparison to those enrolled. Patients collecting data is defined as a patient that records just one entry in any of the HUMA collected variables.

6.2.2. Usability of Fresh Start amongst people with ‘high risk’ or ‘very high risk’ type 2 diabetes.

Usability is to be determined by the following measures recorded over the 12-week assessment period:

- Number of **Video Group Consultations (VGC)** attended per patient
- Number of **Fresh Start** emails opened per patient
- Number of **Blood Glucose** measurements recorded per patient within HUMA
- Number of **Blood Pressure** measurements recorded per patient within HUMA
- Number of **Weight** measurements recorded per patient within HUMA
- Number of **Diabetes Distress Score (DDS)** measurements recorded per patient within HUMA

6.2.3. Acceptability of Fresh Start amongst people with ‘high risk’ or ‘very high risk’ type 2 diabetes.

Acceptability is to be determined by qualitative patient interviews completed by the ICHP team after the 12-week assessment period.

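### SAP 7.5.2 does not summarise emails opened per patient, one of the six patient usability measures, and the interaction counts planned instead are undefined and cannot replace it

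*SAP*

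**What the plan says.** **The measure.** The protocol's outcome table (3.6) and the SAP's variable table (6.1) both list "Number of Fresh Start emails opened" under the primary objective on patient usability, with KD as the source. SAP 6.2.2 makes the unit the patient, "emails opened per patient", over the 12-week assessment period.

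**The analysis.** SAP 7.5.2 sets out mean, SD, median, quartiles and range, per patient and per unit time, for VGCs attended and for glucose, blood pressure, weight and DDS measurements recorded. Emails are not in that list. They receive three outputs of their own:

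- "Number of patients that interacted with all emails"
- "Number of patients that interacted with no emails"
- interactions for each email, glossed as click rates

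The lead-in to these adds that "any additional information may also be presented". The methods table in SAP 7.2 says only "emails metrics as section 7.5.2" and promises frequencies and percentages. Usability tables 4.1 to 4.5 in SAP Appendix 1 cover the other five measures; none covers emails.

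**How emails reach patients.** Protocol 3.4 and SAP 5.2.1 describe two emails a week for the 12-week service. Under the educational emails heading in protocol 3.7, staff sign patients up to the first two emails in the onboarding call, and then: "Sign patients up to full Fresh Start campaign in first VGC". Protocol Appendix 2 agrees that sign-up happens twice, at the start and at the first VGC.

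**The concern.** The outcome is a count of opens for each patient. The planned outputs are two extreme categories of patient and a rate for each email. They differ from the outcome in the event counted (interaction or click rather than open) and in the form of the summary (extremes rather than a distribution). A reader of the report could not tell how many emails a typical patient opened, although engagement is what this feasibility study sets out to measure.

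The terms add a second difficulty. The SAP does not say whether an interaction is an open, a click or either, nor whether *all* means every email sent to that patient or every email in the campaign. Because the full campaign is joined at a VGC, the number sent may differ between patients and may depend on attendance, which is itself a usability measure. The all/none categories could then combine patients with very different exposure to the emails.

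**Working it through.** The plan gives no target, precision or expected value for emails, so there is no figure of its own to reproduce. The check is a comparison of definition with analysis, followed by simple arithmetic.

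**1. Definition against analysis**

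| | SAP 6.1, 6.2.2 | SAP 7.5.2 |
|---|---|---|
| Event | open | interaction (undefined); click for the per-email rate |
| Unit | patient | patient for all/none; email for click rates |
| Summary | count over 12 weeks | two counts and a rate |
| Base | not needed for a count | not stated |

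**2. Emails scheduled per patient.** 2 per week × 12 weeks = 24. The number 24 is derived; the documents do not state it.

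**3. Can the all/none counts give mean opens?** Take the enrolment target of 300. Assume 24 emails each, *interacted* meaning opened, 30 patients in *all* and 60 in *none*. The other 300 − 30 − 60 = 210 opened between 1 and 23 emails each.

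- Lowest mean: (30 × 24 + 210 × 1) / 300 = 930 / 300 = 3.1
- Highest mean: (30 × 24 + 210 × 23) / 300 = 5,550 / 300 = 18.5

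If *interacted* means clicked, the counts say less still about opens. The third output does not close the gap as written, because it is glossed as click rates. Were it to count opens over a known base, summing across the 24 emails would give the mean, but not the SD, median or quartiles that the other five measures receive.

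**4. Effect of the undefined *all*.** Consider a patient signed up to the first two emails only, who opens both, and a full-campaign patient who opens 23.

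| Meaning of *all* | Opened 2, sent 2 | Opened 23, sent 24 |
|---|---|---|
| All sent to that patient | 2/2 = 100%: counts as *all* | 23/24 = 95.8%: does not |
| Full scheduled campaign | 2/24 = 8.3%: does not | 23/24 = 95.8%: does not |

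**5. Illustration under the first meaning.** Let q be the chance of interacting with any one email, assumed equal and independent across emails and patients. The chance of interacting with all k emails is q^k.

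| q | k = 2 | k = 24 |
|---|---|---|
| 0.5 | 0.25 | <0.0001 |
| 0.7 | 0.49 | 0.0002 |
| 0.9 | 0.81 | 0.080 |

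With 300 enrolled, q = 0.9 and an assumed 10% receiving only two emails, the expected *all* count is 30 × 0.81 = 24.3 from that group and 270 × 0.0798 = 21.5 from full-campaign patients. The two-email group is 24.3 / 45.8 = 53% of those labelled *all*. With 5% to 30% receiving only two emails, the share runs from 35% to 81%; at lower q it is higher. The documents give neither q nor the rate of loss before the first VGC, so these figures show direction and range only.

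**The case against.** The strongest reply is that nothing prevents opens from being reported. Protocol 3.11 says that all outcomes will be reported descriptively, with means and SDs or medians and interquartile ranges for continuous variables. SAP 7.1.1 repeats that format for the primary feasibility endpoints, and 7.5.2 leaves room for further email output. A reader might therefore infer too much in concluding that the outcome will go unreported. That stands: the fault is that the section specifying the analysis does not carry the definition through. A general statement and an optional clause do not replace a specified summary when the other five measures have one.

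A reader might also infer that an email opened without a click counts as no interaction. The documents do not show this. The click gloss is attached only to the per-email line, and the all/none lines could count opens. What stands is that the term is undefined. Likewise, percentages and click rates imply some base; it is simply not stated.

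On unequal exposure, the two-email patient is an inference from the staff-action list. The same part of protocol 3.7 has patients told at onboarding to sign up for the emails, the link is also shared during VGC sessions, and protocol 3.4 describes two emails weekly throughout. Missing the first VGC therefore need not end the emails at two. If *all* means the scheduled campaign, the problem in step 4 does not arise. These objections make the exposure point conditional; they do not remove it, because the SAP settles neither question.

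Finally, the analysis is descriptive, with no email threshold, test or progression rule attached. That limits the consequence and is accepted.

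**Conclusion.** The point holds as a minor mismatch between definition and analysis. Emails opened per patient is one of six patient usability measures under a primary objective, not the sole one, and it is the only one of the six without a per-patient summary in SAP 7.5.2 or a table in Appendix 1. This conclusion rests on the text alone.

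The size of the information gap is illustrative: a mean between 3.1 and 18.5 from the all/none counts, assuming 300 patients, 24 emails each, *interacted* meaning opened, and 30 and 60 patients in the two categories.

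The tempting stronger conclusion is that patients who leave early will be counted as fully engaged. The documents support only that this could happen, if *all* means all emails sent to that patient and if some patients receive only the first two. No error rate, power or sample size is affected.

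**What to change.** In SAP 7.5.2:

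- Add emails opened per patient to the list of measures that receive mean, SD, median, quartiles and range.
- Report opens also as a proportion of emails sent to that patient, where KD or sign-up records give the number sent; otherwise as a proportion of the 24 scheduled.
- Report clicks separately and call them clicks, with the base of each rate stated.
- State that *all* means the full scheduled campaign, and show how many patients were never signed up to it. Keep those patients in the all/none categories: restricting the categories to patients who joined the full campaign would condition on VGC attendance and could drop some of the least engaged.

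In SAP Appendix 1, add an email table alongside tables 4.1 to 4.5.

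The cost is SAP wording and slight extra descriptive work, provided that the data exist. The documents name KD as the source for opens but do not say that it holds patient-level opens or numbers sent. The sponsor should confirm this before the text is fixed.
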